**4. Purpose, hypothesis and key questions:**

The proposed study will examine the threshold for nicotine self-administration (NSA) using five different nicotine doses in young adult male and female non-dependent smokers (light and intermittent smokers or LITS). We propose a double-blind, placebo-controlled study that will enroll 195 individuals, targeting a total of 72 completers (36 male and 36 females). In each of the five experimental sessions, smokers will be randomly assigned to one of the five doses of nicotine (0.0125, 0.025, 0.05, 0.1 and 0.2 mg/70 kg). The highest dose, 0.2 mg/70 kg, corresponds to nicotine delivered by about one or two puffs of a cigarette. At the beginning of each experimental session, smokers will sample the assigned both the nicotine dose for that experimental session, and the placebo (saline) dose, followed by the opportunity to choose between nicotine and placebo for a total of ten choices over a 165-minute period. The main outcomes will be threshold dose (the minimum dose of nicotine that is self-administered more than placebo) and the slope of dose-response for nicotine self-administration (changes in nicotine self-administration per unit change in nicotine dose). We will also collect measures of nicotine intake (cotinine), nicotine clearance (3-hydroxycotinine (3-HC) / cotinine), and self-report drug effects.

The following questions will be addressed:

Aim #1: To assess the threshold reinforcing dose and dose-effect curve for IV NSA at low doses in young adult LITS.

Hypothesis #1A: The threshold reinforcing doses for IV NSA will be between 0.0125 to 0.1 mg/70 kg.

Hypothesis #1B: The dose-effect curve for NSA will differ between males and females with relatively flat curve in female smokers.

Aim #2: To assess the threshold and dose-effect curve for the positive and negative/aversive subjective effects of IV nicotine at low doses and its relationship to nicotine reinforcement.

Hypothesis #2 A: The threshold for the positive effects will be between 0.0125 to 0.1 mg/70 kg, for the negative/aversive effect it will be  $\geq 0.1$  mg/70 kg.

Hypothesis #2B: Nicotine reinforcement will be positively correlated with the positive and negatively correlated with the negative/aversive subjective effects of IV nicotine.

Exploratory Aims: To examine the influence of nicotine clearance rate on nicotine reinforcement threshold and dose-effect curve.

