## **12. Data analysis methods:**

Data analyses: The primary analyses will be intent-to-treat and will include all available data on subjects who complete at least one test day. Mixed-effects models will be used to test the study hypotheses. These models allow for different numbers of observations per subject, use all available data on each subject, and are unaffected by randomly missing data. They also provide flexibility in modeling the correlation structure of the data. All data will be checked for normality and transformations will be applied as necessary. Significance level of 0.05 will be used for the main hypotheses and Bonferroni correction will be applied for post-hoc tests and secondary analyses.

Specific Aim #1: Aim #1: To assess the threshold reinforcing dose and dose-effect curve for IV NSA at low doses in young adult LITS. Hypothesis #1A: The threshold reinforcing doses for IV NSA will be between 0.0125 to 0.05 mg/70 kg. Hypothesis #1B: The dose-effect curve for NSA will differ between males and females with relatively flat curve in female smokers.

**Aim #1 Analysis:** The reinforcing effects of nicotine will be determined by the number of IV NSAs in each session, ranging from 0 to 10. The threshold dose for NSA will be determined by the lowest dose of nicotine for which the number of NSAs is significantly greater than those for placebo (saline) (i.e., proportion of NSA significantly higher than 0.5). For assessing the dose-response relationship, the parameters of interest will be the slope and shape of the dose-response curve. The slope indicates the degree to which self-administration changes with an increase in nicotine dose (in other words, sensitivity of NSA to changes in nicotine dose).

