The analysis of Aim #1 will conducted in several steps. First, we will use descriptive statistics and figures to summarize the data. In particular, the number of NSAs for each dose of nicotine will be plotted individually, for the entire sample, and for male vs. female and smokers. This step will allow a visual inspection of both individual and group differences for estimating the threshold dose and the shape of the dose-response curve for nicotine reinforcement. Second, we will fit mixed effects logistic regression models with the proportion of NSAs per session (out of 10) as the dependent variable, dose as a fixed categorical predictor and subject as a random effect. This approach allows us to take into account the correlations between repeated observations on the same individual and to estimate individual deviations from the overall group thresholds.

It also does not assume a specific form of the dose-response relationship and allows us to use all available data on a subject in the unlikely event that a subject fails to complete a session. If a subject fails to complete a session, the total possible number of self-administrations for this subject and session will be adjusted.

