We expect to observe a significant dose effect and will compare the proportion of NSAs at each dose to 0.5 across subject groups. The lowest nicotine dose that has a significantly higher proportion of NSA than 0.5 will be selected as the threshold dose (Hypothesis 1A). To assess the dose-response relationship in the preference for nicotine, polynomial effects of dose (linear, quadratic, cubic) and change-point linear models will be tested in the mixed effects logistic regression model. We anticipate that there will be a significant linear relationship between dose and response rate at lower doses with flattening of the relationship at higher doses. We will use the slope of the dose effect to assess the linear dose effect. Alternative non-linear dose response relationships will be considered if residual plots reveal significant deviations of the models from linearity. Gender differences in the shape of the curve for NSA will be examined in the logistic regression model by including gender main effect and its interactions with dose (Hypothesis 1B). Significant interactions between the group factors and dose will be considered supportive of systematic group differences in the dose-response relationships between groups. If significant interactions are observed, then separate thresholds and curves will be estimated within each subject group.

**Specific Aim #2:** To assess the threshold and dose-effect curve for the positive and negative/aversive subjective effects of IV nicotine at low doses and its relationship to nicotine reinforcement. Hypothesis #2 A: The threshold for the positive effects will be between 0.0125 to 0.1 mg/70 kg, for the negative/aversive effect it will be  $\geq 0.1$  mg/70 kg. Hypothesis #2B: Nicotine reinforcement will be positively correlated with the positive and negatively correlated with the negative/aversive subjective effects of IV nicotine.

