**Aim 2 Analysis:** The subjective-positive effects of nicotine which will be determined by the main dependent variables of scores on the "like the drug" and "want more drug" items of the Drug Effects Questionnaire, ranging from 0 to 100. The negative aversive effects of nicotine will be determined by the "dislike the drug" and "lightheaded/dizzy" item of the DEQ. The analysis for Specific Aim #2A will be similar to the analysis described for Specific Aim #1A except that the dependent variables will be continuous and thus we will use random effects linear regression. Gender effects will be explored also as outlined for Specific Aim #1B. Prior to analysis, we will also assess the distribution of the DEQ items and apply transformations as necessary. Furthermore, the mean ratings at each dose will be compared to 0. To assess the

relationship between nicotine reinforcement and positive subjective effects, and between nicotine reinforcement and negative subjective effects (Specific Aim #2B), we will use mixed effects models with the proportion of NSAs per session as the dependent variable, positive (negative) subjective effects in response to the sample dose as the main predictor of interest (in separate models for positive and negative effects). Nicotine dose, gender and the interactions among subjective effects, dose and gender will also be assessed. Non-significant interactions will be dropped from the models via backward elimination subject to the constraint that the models will be hierarchically well-formulated at each step. Statistically significant associations between subjective effects and NSA across doses and gender are expected but we will also explore whether these relationships vary by gender and dose.

**Exploratory Aim #1:** To examine the association between baseline 3HC/cotinine ratio and nicotine reinforcement threshold. To test this hypothesis, correlation analysis including 3 HC/cotinine ratio and nicotine reinforcement threshold will be performed in the total sample as well as in subgroups (male vs. female smokers).

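### Exploratory Aim #1 correlates the metabolite ratio with a per-subject threshold that the plan never defines and that ten choices per dose measure poorly; ratio terms in the planned mixed model would serve better

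*Combined protocol and SAP*

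**What the plan says.** Section 4 of the combined protocol and SAP gives the exploratory aim as: "To examine the influence of nicotine clearance rate on nicotine reinforcement threshold and dose-effect curve". It names two targets, the threshold and the curve.

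Section 12, Exploratory Aim #1, gives one analysis: "correlation analysis including 3 HC/cotinine ratio and nicotine reinforcement threshold will be performed in the total sample as well as in subgroups", the subgroups being male and female smokers.

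Section 12, Aim #1, defines the threshold: "The lowest nicotine dose that has a significantly higher proportion of NSA than 0.5 will be selected as the threshold dose". The test behind it is made at group level; the investigators "will compare the proportion of NSAs at each dose to 0.5 across subject groups". The model has "dose as a fixed categorical predictor and subject as a random effect", and the text says that it can also estimate how far individuals depart from the group threshold. Individual plots are to be inspected as a descriptive first step.

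On the amount of data per subject: "The reinforcing effects of nicotine will be determined by the number of IV NSAs in each session, ranging from 0 to 10". Section 4 gives five sessions, one per dose.

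**The concern.** The outcome in the planned correlation does not exist until someone decides how to assign a threshold dose to one subject. The only written criterion is a hypothesis test designed for the whole sample. Moved to a single subject, it rests on ten binary choices.

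Three things follow. The outcome is noisy. It is undefined for any subject with no qualifying dose. The handling of those subjects would be decided after the data are seen, although it can change the result. A null correlation would then say little about nicotine clearance. The other half of the stated aim, the dose-effect curve, would have no planned analysis.

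**Working it through.** **Inputs from the documents.** 72 completers, 36 per sex (Section 7); five doses with ten choices each (Sections 4 and 12); null 0.5, meaningful preference 67%, two-sided alpha 0.05 (Section 12, rationale for sample size).

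**The plan's own figure.** The plan states 80% power for 67% against 50% with 72 subjects. Taking one binary outcome per subject, the exact binomial test rejects at 45 of 72 or more. Power is 82.6% at 0.67 and 81.0% at two-thirds; with a continuity correction it is 80.5% and 78.7%. The figure reproduces. It covers Aim 1, and the plan states no power for the exploratory aim.

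**The stated rule applied to one subject at one dose (X out of 10).**
- Two-sided p = 2 × P(X ≥ x | 10, 0.5). For x = 8, 2 × 0.0547 = 0.109. For x = 9, 2 × 0.0107 = 0.021. So at least 9 of 10 is needed.
- P(X ≥ 9 | p) = 10 p⁹(1 − p) + p¹⁰. At p = 0.67: 0.0898 + 0.0182 = 0.108. At 0.80 it is 0.376, and at 0.90 it is 0.736.
- Chance of no threshold when the true preference is p at all five doses: (1 − 0.108)⁵ = 0.565 at 67%, 0.095 at 80%, 0.001 at 90%.
- Chance of a false threshold with no preference at any dose: 1 − (1 − 0.0107)⁵ = 0.053.
- If Bonferroni over five doses were applied (0.05/5 = 0.01), 10 of 10 would be needed. The chance per session is then 1.8%, 10.7% and 34.9% at 67%, 80% and 90%.
- For 80% power in one subject at 67% preference, 67 choices per dose would be needed.

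**What the model's individual deviations give.** With categorical dose and one subject effect, logit(p) for subject i at dose d is β_d + b_i. The term b_i moves all five doses by the same amount. With complete data it ranks subjects by total nicotine choices out of 50. A dose could be derived from it, but the plan states no rule for doing so.

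**Simulation, step-shaped preference.** The assumptions are mine, not the plan's: true thresholds spread evenly over the five doses; choice probability 0.5 below a subject's threshold and 67%, 80% or 90% at or above it; latent correlation of ratio and threshold 0.35; subject bias SD 0 or 0.5 on the logit scale; observed threshold the lowest dose with at least 9 of 10; 1,500 trials per setting, so the Monte Carlo standard error is at most √(0.25/1500) = 1.3 points. With true thresholds known, power would be 79-82%.

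| Bias SD | Preference | No threshold | Correct dose | Power, dropped | Power, ranked above top dose | Power, total choices |
|---|---|---|---|---|---|---|
| 0 | 67% | 70% | 11% | 9% | 10% | 38% |
| 0 | 80% | 29% | 37% | 32% | 39% | 63% |
| 0 | 90% | 7% | 72% | 62% | 70% | 72% |
| 0.5 | 67% | 65% | 13% | 8% | 9% | 15% |
| 0.5 | 80% | 34% | 35% | 23% | 26% | 38% |
| 0.5 | 90% | 10% | 65% | 48% | 53% | 55% |

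Further simulations under other assumed effects gave about 10-15% with subjects lacking a threshold dropped, 26-54% with them ranked above the top dose, and 44-92% using all choices. The order was the same in every setting tried, although at 90% preference the last two columns hardly differ.

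**Limit even with perfect thresholds.** For 80% power, |r| = tanh(2.802/√(n − 3)): 0.33 at n = 72 and 0.45 at n = 36.

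**The case against.** A reader might infer that the plan tests each subject's ten choices for significance and excludes subjects without a threshold. The documents say neither. The test is described at group level, and for individuals Section 12 offers plots and model-based deviations. This stands: the documented defect is that the per-subject threshold and the no-threshold case are undefined. The 9-of-10 calculation shows what happens if the only written criterion is used. If the deviations are used, much less power is lost, but the correlation is then with overall nicotine preference, not with a threshold dose.

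A reader might also infer that ten choices cannot identify a threshold, so that a real clearance effect would be missed. That is too strong. At 90% preference, 65-72% of subjects are placed at the right dose and power is 48-70% in the table. Against this, the plan's own planning effect is 67%, and its preliminary study found nicotine choices no more frequent than saline choices overall.

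The size of the power gain is also open to challenge. It depends on the assumed curve, the spread of thresholds and subject bias, none of which the documents give. The all-choices test simulated here used each subject's overall proportion, which measures general preference. The power of the full model with ratio-by-dose and ratio-by-sex terms was not computed. Both points stand, so the ranges are indicative only.

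Finally, the aim is exploratory and no power is claimed for it. That governs severity. It is not a reason to leave the outcome undefined.

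**Conclusion.** The point holds in limited form. Exploratory Aim #1 needs a threshold for each subject that the plan does not define. The group criterion transferred to one subject is weak at the plan's own effect: 10.8% per session, and a 56% chance of no threshold for a subject at 67% on every dose. These figures are exact, given independent choices and an unadjusted two-sided 0.05 test.

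The loss of power relative to using all choices is consistent in direction, but its size rests on assumed scenarios and shrinks as preference becomes strong. Separately, and without any assumption, the dose-effect-curve half of the aim in Section 4 has no analysis in Section 12.

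Severity is low. The documents do not support reading this as a threat to Aims 1 or 2, to the sample size or to safety.

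**What to change.** In Section 12, replace the total-sample and by-sex correlations with the (log) 3-HC/cotinine ratio as a continuous predictor in the mixed logistic model already planned for Aim 1. Include its main effect, a ratio-by-dose term and a ratio-by-sex term, and use all subjects and sessions. Report model-based group thresholds at a low and a high value of the ratio, fixed in advance. The ratio-by-dose term supplies the missing curve analysis, and the ratio-by-sex term replaces two separate correlations at n = 36.

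If a per-subject threshold is kept as a descriptive summary, write down how it is assigned, and rank subjects without one above the top dose instead of dropping them.

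The cost is a few sentences in Section 12. No new data, visits or subjects are needed, so this is a free improvement.

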### **13. Risks and benefits:**

#### **Potential risks**

There are potential risks, discomforts and inconveniences associated with the participation in this study. These may be due to nicotine administration, blood drawing, and other study procedures.

- 1) The administration of nicotine may cause cardiovascular, autonomic, and gastrointestinal complications. Large doses of nicotine may cause nausea, vomiting, abdominal pain, hyper salivation, diarrhea, dizziness, confusion, hearing and vision problems, syncope, seizures, hypotension, irregular pulse, and death. However, these toxic effects occur at doses 10-20 times that which will be used in our study. Other potential risks from this study include administering a drug that has addictive potential. However, since only subjects with an extensive history of cigarette use are to be included, we will not be exposing subjects to the risks of nicotine for the first time. Additionally, we are not enrolling subjects who are seeking treatment to quit smoking. Over the last 5 years, we have administered nicotine intravenously to more than 100 smokers and have not encountered any adverse events from nicotine.
- 2) Blood Drawing: Subjects will have approximately 200 ml of blood drawn as a result of their participation in the study. Blood drawing can cause some pain and may result in bruising.
- 3) Study procedures: On the test days, subjects will not be able to smoke for 10 hours. During this cigarette abstinence period, subjects may experience symptoms of nicotine withdrawal such as craving cigarettes, mild anxiety, restlessness, irritability, difficulty concentrating, loss of energy, and excessive hunger.

#### **Protection of Subjects**

In order to participate in a study, each subject must give informed consent. All potential risks will be described in detail to the subjects in the consent form. The personnel in the laboratory have

been certified in either Advance Cardiac Life Support (ACLS) or Basic Life Support. If a problem arises, the subject will be treated immediately.

Confidentiality in this study is of the utmost importance to us. All information obtained will be stored in coded form. The names of the subjects will be used in hospital records.

## **14. Safety**

Prior to initiating any research activity, each subject must give informed consent. Before the study, the subjects will be informed about all potential risks of the study. Our inclusion and exclusion criteria will be applied by experienced professionals who will be carefully trained and monitored in order to accept only appropriate subjects into the study. Thus, effective screening will exclude subjects who would be placed at a greater risk. Eligibility is determined by the medical and psychiatric history, drug use history, the physical examination, and the laboratory studies done prior to beginning this research protocol.

For nicotine administration sessions, a physician will be present and subjects will be attached to a cardiac monitor as well as a blood pressure and heart rate monitoring device. An IV catheter will be in place throughout the session. Subjects will be administered nicotine only if the systolic blood pressure is <150 mmHg and heart rate is <100 beats/minute. Subjects will be terminated from the study if the blood pressure at any time is >170/110 mm Hg, the heart rate is >120 beats/min, or if they develop signs and symptoms compatible with nicotine toxicity. Subjects will remain in the laboratory for at least an hour after the last nicotine administration. These procedures have been developed as part of our IND for IV nicotine.

Confidentiality will be protected by having records identified by code number only with the master list including names kept in a sealed envelope in a locked file in the Principal Investigator's office and by the pharmacy. Subjects will be given telephone numbers to call in case of emergency, 24 hours a day.

**14.1 Potential benefits of the proposed research to the subjects and others.** There will be no direct benefit to subjects participating in this study. However, subjects will receive complete medical and psychological evaluation. Cigarette smokers will be given anti-smoking literature and treatment resources will be provided for smoking cessation.

**14.2 Importance of the knowledge to be gained.** This proposed study may help to develop new and more effective tobacco control policies. We believe that the risk/benefit ratio for this study is acceptable, and that the benefits of the proposed studies outweigh the potential risks to subjects.

**14.3 Data safety and monitoring plan:** The Principal Investigator will conduct a review of all adverse events and determine the attribution and grade of severity of the adverse event by using the following scales:

Attribution of Risk Categories:

Definite: Adverse event(s) will clearly be related to investigational agent(s) or other intervention

Probable: Adverse event(s) will likely be related to investigational agent(s)

Possible: Adverse event(s) may be related to investigational agent(s)

Unlikely: Adverse event(s) will doubtfully be related to investigational agent(s)

Unrelated: Adverse event(s) will clearly not be related to the investigational agents(s)

Grades of Risk:

- 0: No adverse event or within normal limits
- 1: Mild adverse event
- 2: Moderate adverse event
- 3: Severe adverse event resulting in hospitalization or prolongation of existing hospitalization, a persistent or significant disability/incapacity, or a congenital anomaly/birth defect
- 4: Life-threatening or disabling adverse event
- 5: Fatal adverse event

Serious adverse events (SAEs) include any untoward medical occurrence that at any dose results in death or the immediate risk of death, hospitalization or the prolonging of an existing hospitalization, persistent or significant disability/incapacity or a congenital anomaly/birth defect. Subjects will be terminated from participation if the investigator feels that subjects' health or well-being may be threatened by continuation in the study. Serious unanticipated and anticipated adverse events will be reported within 48 hours to the VA Hospital and Yale IRB, and NIDA. We will directly report to the FDA, whenever their magnitude or frequency exceeds expectations.

The risk associated with participating in this study is moderate, because nicotine administered may be associated with mild side effects. Serious side effects associated with this treatment are not expected. This project will be monitored by a Data and Safety Monitoring Board (DSMB) because the study involves double-blind treatment of smokers with nicotine. This board is composed of persons not otherwise affiliated with the clinical study who are experienced in various aspects of the conduct of clinical trials for the treatment of addictive disorders. We propose three investigators located here in Connecticut who are not directly involved in this study – [name]., [name]., and [name]. as the members of the DSMB. The members of the DSMB and all study Investigators will complete Conflict of Interest forms created by Yale's IRB in accordance with NIH guidelines.

In order for the DSMB to fulfill its mission of assuring the safety of human subjects and the scientific integrity of the studies conducted, the Board will have access to accumulating study outcome data in a manner that will protect its confidentiality and preserve its statistical integrity. The Board will examine accumulating data to assure that the risks and benefits of participation remain acceptable and that the results of the study will be considered scientifically reliable. The conditions under which the Board will examine this data are described below. This monitoring will be consistent with NIH policy regarding the protection of human subjects in research, and FDA guidance on statistical practices for clinical trials (ICH E9) and good clinical practices (ICH E6). In general, the data to be reviewed will include screening data, baseline data, efficacy data, and safety data.

The study will be monitored for safety in an ongoing way as well as three times each year formally by the DSMB. The P.I. will attend an initial part of this meeting to present the study's adverse events and ongoing subject accrual, as well as any potential study design changes under consideration. The remainder of the meeting will not include any direct study personnel until the end of the meeting, when the DSMB will convey directly to the P.I. any safety or study conduct concerns, as well as requests for potential interim analyses.

Following each DSMB meeting written minutes will be prepared and distributed summarizing any recommendations. These written reports will insure timely communication with the study P.I. with preparation of any protocol amendments necessary. After each DSMB meeting, this written report will describe all recommendations including additional safety steps. The FDA adverse drug experience reporting timelines will be utilized as timelines to disseminate feedback from the DSMB to the principal investigator and sub investigators. That is, three days for acute circumstances and ten days for non-acute circumstances.

**15. Informed consent:** Subjects will be recruited from the New Haven area by newspaper advertisements and fliers. Interested subjects will be informed about the study over the telephone and asked for current use of drugs and medical problems. If subjects are interested, they will then come into the clinic for a full screening evaluation. Upon arrival, a research assistant will read the detailed consent form and will ask questions to make sure that the subjects understand the procedure and their rights and informed consent will be obtained.

**16. Information Security/Confidentiality:** Confidentiality in this study is of the utmost importance to us. All information obtained will be stored in coded form.

Personally identifiable information (PII) and protected health information (PHI) that is obtained from subjects or about them will be protected by the research team who will follow all guidance provided in the following VHA HANDBOOKS and DIRECTIVE:

- VHA HANDBOOK 1605.1, PRIVACY AND RELEASE OF INFORMATION Dated May 17, 2006
- VHA HANDBOOK 1907.01, HEALTH INFORMATION MANAGEMENT AND HEALTH RECORDS Dated August 25, 2006
- VHA HANDBOOK 6500, INFORMATION SECURITY PROGRAM Dated September 18, 2007
- MEMORANDUM FOR UNDER SECRETARIES, ASSISTANT SECRETARIES AND OTHER KEY OFFICIALS, SUBJECT: Protecting Information Security and Privacy Dated February 27, 2009
- VHA HANDBOOK 1200.12, USE OF DATA AND DATA REPOSITORIES IN VHA RESEARCH Dated March 9, 2009

All data collected will be the property of the Department of Veterans Affairs whether in paper or electronic form and will be secured utilizing the following methods:

Paper:

- All paper documents will be stored on VA property unless authorized by the Director, Information Security Officer, and Privacy Officer in writing.
- All paper documents will be locked in an approved file cabinet with only members of the research team having access.

Electronic:

- All information in electronic form will be stored on VA servers behind the VA firewall.
- All portable media will meet or exceed FIPS 140-2 compliance and encryption. And will be approved in writing by the Information Security Officer.

The location(s) where information will be stored is (are) Building 35, rooms 19 and 39

The people or agencies that will have access to the information are the study investigators.

No information related to this research will be released to any third party or disclosed outside of the VHA – except as required or permitted by law.

Research records will have identifiers removed and will be stored with a code number linked to subjects. The code will not be derived from any personal identifiers. The key to the code will be kept in a locked file cabinet, located in Bldg 35, room 19. Subjects' identity will not be revealed in any reports or publications resulting from this study.

**17. Location of Study:** This study will be conducted in Ward G9W (the Biostudies Unit) located in Building 1 at the West Haven VA Medical Center.

**18. Payment:** Subjects will be paid \$30 for participating in the screening and \$130 for each of the 5 lab sessions and \$20 for transportation for each of the 5 test sessions. If the subjects choose to terminate a session prematurely, or a session is terminated early for medical reasons, they will receive full payment for that day. If they become ineligible to continue in the study due to non-compliance with study procedures, they will only be paid for the portions of the study in which they have participated. Subjects may also earn \$20 for referring people they know who also smoke cigarettes and are eligible for study participation. A contingency payment of \$20 will also be given for transportation for a visit that wasn't fulfilled in the outlined time frame within the protocol. Subjects may be paid up to \$780 if all parts of the study are completed.

**19. Funding Source:** An RO1 grant from NIDA (pending).

**20. Duration:** The new study design will take approximately 3 years to complete.

